Transcranial Direct Current
Stimulation for Post-stroke Gait
Rehab

NCT03666533

July 13, 2023

Simultaneous transcranial direct current stimulation and gait training for chronic stroke
NCT 03666533

Abbreviated Protocol (from last IRB approved version - 07/2023)

SPECIFIC AIMS Gait deficits following stroke are prevalent and frequently persistent after stroke. Current rehabilitation methods fail to restore normal gait for many stroke survivors. Those who have persistent gait deficits following stroke even after intensive rehabilitation efforts tend to be more dependent on caregivers for assistance with ADLs, demonstrate limitations in household and/or community ambulation, are at higher risk for falls, and report poor quality of life (QOL). One promising treatment method that warrants further investigation is transcranial Direct Current Stimulation (tDCS), a form of non-invasive brain stimulation (NIBS). If found to be effective, tDCS is readily deployable into the neurorehabilitation clinical setting because of its safety, ease of set-up and ability to be paired with other established and effective gait rehabilitation methods. The purpose of this current study is to develop treatment methods that improve gait for those with persistent deficits following stroke. In the proposed study, we will compare the response to active tDCS+gait training versus sham tDCS +gait training. Gait training will be provided within a virtual reality (VR) gait training system and overground and will ensure a consistent, repeated motor learning-based pattern of practice. AIM 1: Determine whether the combination of simultaneous tDCS and gait training produces superior improvement in gait performance than gait training alone. Hypothesis 1: There is an additive advantage in combining tDCS and gait training in improving gait performance in chronic stroke survivors. AIM 2: Characterize the neuroplastic brain changes in response to bihemispheric tDCS combined with gait training. Hypothesis 2: The combination of gait training and tDCS results in a greater increase in corticospinal excitability and strengthened functional connectivity compared with gait training alone. AIM 3: Identify factors that predict gait improvement in response to tDCS with gait training. Hypothesis 3a: Greater gait improvement in response to bihemispheric tDCS with gait training is related to the following combination of baseline factors 1) corticospinal tract (CST) lesion load; 2) greater motor abilities of the affected lower extremity; 3) greater corticospinal excitability; 4) greater functional connectivity; 5) higher integrity of the stroke-affected corticospinal tract; and, 6) lesion type (cortical, subcortical, brain stem). Hypothesis 3b: Greater gait improvement in response to bihemispheric tDCS is dependent on the tDCS-induced electrical current density at the targeted cortical areas in the primary motor cortex for lower extremities.

Study design overview This study is testing the efficacy of utilizing tDCS during gait training for individuals with chronic stroke (>6 mo post-stroke) who demonstrate an abnormal gait pattern. This is a randomized controlled multi-session study to test the potential benefit of combining tDCS and gait training for individuals with chronic gait deficits after stroke. The key exclusion criteria will be more than one stroke, contraindications for transcranial magnetic stimulation, and presence of implanted medical devices such as cardiac pacemaker or vagus nerve stimulator. .

Study intervention Subjects participated in 10 treatment sessions, a baseline testing (includes MRI), a mid-treatment testing session, a testing session after the 10th treatment session (includes MRI) and a 6-week follow-up testing visit. Clinical outcome measures were collected by a trained study staff who is not involved in therapy and blinded to group allocation. Subjects will be randomly allocated to either Treatment Group 1) active tDCS+gait training or Treatment Group 2) sham tDCS+gait training. Each VR gait training session lasted 30 minutes and tDCS will be “on” for the first 15 minutes while the subject simultaneously participates in gait training with guidance of a study physical therapist. Immediately after VR+tDCS training,

subjects participated in 30 minutes of overground training guided by a physical therapist. Home exercises were assigned to be completed on non-training days and reinforced in-person therapy training. Both, the subject and the study staff who is delivering therapy were blinded to group allocation.

Aims 1 and 2 analysis: We directly compare pre to post changes for gait speed and paretic single limb stance duration between the two groups. Similarly, secondary outcome measure changes are being compared between the study groups. We compare trajectories of changes in primary and secondary outcome measures afforded by longitudinal measurement through the course of study participation, using mixed models and the analysis of Treatment Group by time interaction effects. Time is considered as a categorical variable as well as modeled with random slope parameters. Two-sample comparisons of change values are conducted with t-tests or nonparametric methods such as Mann-Whitney U tests.

Aim3 analysis: We correlate change in clinical gait performance measures in response to intervention with baseline variables describing the structural integrity of the corticospinal tracts, functional brain connectivity and lower limb motor abilities. We also explore regression analyses where changes in gait measures is modeled as a dependent variable, and include predictors such as baseline TMS measures (MEP-rc), DTI measures, functional connectivity, motor ability measure and electrical field estimate values.

Inclusion and Exclusion Criteria

Inclusion criteria

- Medically stable and at least 6 months after first ever stroke
- Cognition sufficiently intact to give valid informed consent
- Ability to follow two stage commands.
- Sufficient endurance to participate in the study.
- Age >18
- Observable stance gait deficit while walking on level surface.

Exclusion Criteria

- Acute or progressive cardiac, renal, respiratory, neurological disorders or malignancy.
- Any psychiatric diagnosis or active psychological condition
- More than one ischemic stroke or stroke affecting both sides
- Lower motor neuron damage or radiculopathy
- No observable gait deficit during ambulation
- Presence of implanted medical devices such as cardiac pacemakers and defibrillators, intrathecal drug delivery pumps, or spinal cord, vagus nerve or similar stimulators, or cochlear implants
- Presence of metallic hardware in close contact with the TMS coil such as intracranial implants, aneurysm clips, plates, electrodes
- Past history of seizures or unexplained loss of consciousness
- Family history of medication refractory epilepsy
- History of substance abuse within the last 6 months

- Chronic sleep deprivation, ongoing untreated sleep disorder
- Pregnancy or pregnancy planning during the study period
- Inability to understand English.
- Activity tolerance insufficient to complete VR treadmill training.

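### Two implied primary outcomes serve one Aim 1 superiority claim, and the public text shows no alpha, deciding test, multiplicity control or success rule

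*Combined protocol and SAP*

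**What the plan says.** Specific Aims states one Aim 1 question and one Hypothesis 1, both about gait performance as a whole. Study intervention provides for a baseline test, a mid-treatment test, and "a testing session after the 10th treatment session (includes MRI) and a 6-week follow-up testing visit".

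The Aims 1 and 2 analysis section opens with: "We directly compare pre to post changes for gait speed and paretic single limb stance duration between the two groups". It continues: "Similarly, secondary outcome measure changes are being compared between the study groups". The contrast makes the two named outcomes primary by implication, although no list says so.

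The same outcomes are then analysed a second way: "We compare trajectories of changes in primary and secondary outcome measures afforded by longitudinal measurement through the course of study participation". The method for this second analysis is given as "using mixed models and the analysis of Treatment Group by time interaction effects". On the coding of time it says: "Time is considered as a categorical variable as well as modeled with random slope parameters". On the change comparison it says: "Two-sample comparisons of change values are conducted with t-tests or nonparametric methods such as Mann-Whitney U tests".

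The public text gives no alpha, sidedness, order of outcomes, multiplicity adjustment or rule for success. It also gives no sample size or power.

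**The concern.** One efficacy claim rests on two outcomes. Each can be tested by a t-test or a rank test of change, with no rule for choosing, and by a mixed-model interaction. The section does not say which result decides Hypothesis 1.

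The error rate of the Aim 1 claim therefore depends on a rule that the reader cannot see. Suppose gait speed and stance duration disagree, or the t-test and the mixed model disagree. The public text then offers no way to tell a planned positive result from a selected one.

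The planned change test is also unadjusted for the baseline value, although that value is collected. This gives away precision that could pay for multiplicity control.

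**Working it through.** **Inputs.** From the documents: two outcomes, one claim, two arms, a pre-to-post comparison, and a t-test or Mann-Whitney test. Assumed, because the documents do not give them: two-sided 5% per test, correlation between the two change scores from 0 to 0.9, and for power an illustrative 80% per outcome. The plan states no figure to reproduce.

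**1. Either change test is enough.** With independent outcomes the rate is 1 − 0.95² = 0.0975. With correlation r it is 1 − P(|Z1| < 1.96 and |Z2| < 1.96) under a bivariate normal. In favour of active tDCS alone it is 1 − P(Z1 < 1.96 and Z2 < 1.96), against a nominal 2.5%. Both outcomes significant, by inclusion-exclusion, is 0.05 + 0.05 − the either rate; at r = 0.9, 0.10 − 0.0704 = 0.0296. Under Holm, the chance of any false positive when neither outcome has an effect is the either formula with 2.241 in place of 1.96.

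| Correlation | Either, two-sided | Either, favouring active | Both significant | Holm |
|---|---|---|---|---|
| 0 | 9.75% | 4.9% | 0.25% | 4.9% |
| 0.5 | 9.1% | 4.5% | 0.9% | 4.7% |
| 0.8 | 7.8% | 3.9% | 2.2% | 4.0% |
| 0.9 | 7.0% | 3.5% | 3.0% | 3.6% |

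Simulated t-tests with an assumed 10, 20 and 30 per arm gave 9.7-9.9%, 8.9-9.2% and 6.9-7.1% for the two-sided either rule at correlations 0, 0.5 and 0.9. The result hardly depends on the unknown sample size.

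**2. Free choice between t-test and Mann-Whitney.** Simulation with normal data and an assumed 20 per arm gave 11.5%, 11.0%, 9.4% and 8.5% at correlations 0, 0.5, 0.8 and 0.9. That is about 1-2 points above the either column. The addition depends on the distribution and is larger for heavy-tailed or skewed data.

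**3. Power cost of control.** At 80% power and two-sided 5%, the standardised effect is 1.960 + 0.842 = 2.802.
- Holm, other outcome without effect (worst case): Φ(2.802 − 2.241) = 0.712. Keeping 80% would need ((2.241 + 0.842)/2.802)² = 1.21 times the participants.
- Holm, other outcome equally powered: at correlation 0, 0.712 + (0.800 − 0.712) × 0.712 = 0.775; at correlation 0.9, 0.751.
- Both must succeed: 0.80² = 0.64 at correlation 0, rising to 0.75 at 0.9.

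**4. What baseline adjustment recovers.** With equal baseline and follow-up variances σ² and within-person correlation ρ, the change-score variance is 2σ²(1 − ρ) and the adjusted variance is σ²(1 − ρ²). Their ratio is (1 + ρ)/2. Power at the 2.5% level in the worst case is Φ(2.802/√((1 + ρ)/2) − 2.241).
- ρ = 0.6: ratio 0.80, power 0.813
- ρ = 0.8: ratio 0.90, power 0.762
- ρ = 0.9: ratio 0.95, power 0.737

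**The case against.** The strongest objection is that the document is headed as an abbreviated protocol. It also omits sample size, power and the list of secondary outcomes, so a missing alpha or success rule is weak evidence that the plan has none. That stands. A reader might infer that the trial has no rule; the documents support only that the public text does not show one.

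Second, no section says that either outcome suffices. A reader might take 7-10% as this trial's error rate, but it holds only under an either-counts rule. If both must succeed there is no inflation. And since Aim 1 claims superiority, a result favouring sham cannot support it, so the directly relevant figure is 3.5-4.9% against 2.5%. The relative inflation is similar.

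Third, a reader might add the interaction and slope tests as further chances to win and arrive at rates well above 10%. The documents do not support that. The mixed models are given the separate purpose of comparing trajectories, and the sentence on random slopes can describe one model rather than a second treatment test. Any figure would also need an assumed visit schedule and covariance. Nor do mixed models offer the only route to a higher rate: an open choice between t-test and Mann-Whitney is enough. That choice may, however, be meant as an ordinary response to the distribution of the data.

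Finally, the change comparison comes first and may be intended as the main analysis. Granting that, the question of two outcomes is still unanswered.

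**Conclusion.** The point holds as a gap in the public text. Two implied primary outcomes serve one superiority claim, each tested by unadjusted change and again by interaction, and nothing shown fixes the deciding test or the success rule.

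The size is conditional. If either change test at two-sided 5% counted, the rate would be about 7-10% in either direction, or 3.5-4.9% against 2.5% in favour of active tDCS, over outcome correlations 0.9 to 0. Free choice of test would add about 1-2 points with normal data. Under a both-must-succeed rule with one named test each, the rate cannot exceed 5%, and is 0.25-3.0% over this range when neither outcome has an effect.

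This should be fixed. Confidence is medium, because the full protocol may already contain the rule.

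**What to change.** For each of the two outcomes, name one confirmatory analysis: the active-minus-sham difference at the test after the 10th session, adjusted for the baseline value already collected. This replaces the unadjusted change test. State an overall two-sided 5% and choose one rule:
- Holm: the smaller p-value at 2.5% and, if that succeeds, the other at 5%.
- An order of the two outcomes declared in advance.
- A statement that both must succeed.

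Label the Mann-Whitney, interaction, slope and 6-week analyses as supportive and unable alone to carry the Aim 1 claim. Naming the change t-test as the single deciding test would control the error equally well; baseline adjustment is preferred for its precision.

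The cost is a few sentences and no new data. Under Holm, an outcome with an illustrative 80% power keeps about 75-78% if the other is equally powered, and 71% if the other has no effect. Baseline adjustment brings that 71% to about 74-81% at within-person correlations 0.9 to 0.6, assuming equal variances at the two visits. Requiring both outcomes lowers the chance of success to 64-75% when each has 80%. Under a declared order, the second outcome is tested only if the first succeeds.

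If the full protocol already holds a rule, publish it. Study intervention is partly in the past tense ("Subjects participated in 10 treatment sessions"), so data collection may be well advanced. Date any new rule before an unblinded group comparison. If such comparisons have already been seen, a new rule gives no error protection and should be disclosed as post hoc.

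### The pre-to-post change test uses only participants tested at both visits, and the plan does not say whether it or the planned mixed model decides Aim 1.

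*Combined protocol and SAP*

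**What the plan says.** The paragraph on the analysis of Aims 1 and 2 in the combined protocol and SAP describes two approaches to the same primary outcomes.

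- **A direct comparison of change:** "We directly compare pre to post changes for gait speed and paretic single limb stance duration between the two groups". The last sentence of the paragraph gives the method: "Two-sample comparisons of change values are conducted with t-tests or nonparametric methods such as Mann-Whitney U tests".
- **A longitudinal comparison** of primary and secondary outcomes, "using mixed models and the analysis of Treatment Group by time interaction effects". On the coding of time: "Time is considered as a categorical variable as well as modeled with random slope parameters".

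The Study intervention section lists the visits after baseline: "a mid-treatment testing session, a testing session after the 10th treatment session (includes MRI) and a 6-week follow-up testing visit". Allocation is to two arms: "Subjects will be randomly allocated to either Treatment Group 1) active tDCS+gait training or Treatment Group 2) sham tDCS+gait training".

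The text does not say which analysis decides Aim 1. It defines no analysis population, gives no rule for missing outcomes and states no expected dropout. The document calls itself an "Abbreviated Protocol (from last IRB approved version - 07/2023", so a fuller version may hold more.

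**The concern.** A change value needs both a baseline and a post-session-10 measurement. A participant who stops during the 10 sessions and is not tested afterwards has none, and without imputation drops out of the t-test or Mann-Whitney test. A baseline result, and possibly a mid-treatment one, then goes unused in that comparison.

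Two things are at stake. First, participants tested at both visits are no longer the randomised groups. If stopping depends on early response, and does so differently by arm, the difference among them is biased. Second, even when stopping is balanced, some information already collected is lost.

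The mixed model over the same visits limits both problems, but the plan does not say that its baseline-to-post contrast answers the Aim 1 question. Two unranked analyses on different sets of participants can disagree, and nothing says which one prevails.

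**Working it through.** **No plan figure to reproduce.** The documents give no N, SD, effect, alpha or dropout rate. Every number below is an illustration under stated assumptions.

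**Step 1. Who enters each analysis**

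| Participant tested at | Change-score test | Mixed model, categorical time |
|---|---|---|
| Baseline, mid, post | yes | yes |
| Baseline, mid | no | yes, two visits |
| Baseline only | no | baseline only; adds little |

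**Step 2. When the change test is biased.** Let σ be the SD at each visit and ρ the correlation between any two visits, assumed equal.

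- Variance of a change = 2σ²(1−ρ).
- Covariance of post change with mid change = σ²(1−ρ).
- Slope of post change on mid change = σ²(1−ρ) / [2σ²(1−ρ)] = 0.5.

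So if low mid-treatment responders leave, the mean post change of those who stay rises by half the rise in their mean mid change. If the rise is equal in both arms it cancels in the difference. If it is unequal, the remainder is bias. A likelihood model that conditions on the mid-treatment value removes this bias when dropout depends only on observed values.

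**Step 3. Size when dropout differs by arm**

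*Poor early responders leave in the active arm only, no true effect.* Assumed: 20-30 per arm, SD 0.25 m/s, ρ 0.8-0.9. Two simulations, the first with 3,000 trials per setting:

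| Missing overall | Bias, change test | Type I error, change test | Type I error, likelihood model |
|---|---|---|---|
| 9-17% | 0.012-0.029 m/s | 5.6-9.4% | 4.4-4.8% |
| 16-20% | about 0.02-0.03 m/s | 7.6-9.3% | 4.4-4.9% |

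With equal arms and all the loss in one, 16-20% overall means 2 × 16 = 32% to 2 × 20 = 40% of the active arm.

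*Poor early responders leave in both arms, at three times the rate in sham.* Assumed: 15 or 25 per arm, ρ 0.7 or 0.9, true difference 0.40 SD; 4,000 trials per setting.

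| Dropout | Change-test estimate (SD) | Mixed-model estimate (SD) |
|---|---|---|
| 10% | 0.37-0.39 | 0.40 |
| 20% | 0.31-0.36 | 0.39-0.40 |
| 30% | 0.24-0.31 | 0.40-0.41 |

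The bias can therefore run either way.

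**Step 4. Size when dropout is balanced.** In the second set of simulations, with dropout completely at random or following the same rule in both arms, both estimates stay near 0.40. The mixed-model standard error is only about 1-4% smaller. For example, with ρ = 0.7, 25 per arm and 20% missing at random, it is 0.241 against 0.248, and (0.248 − 0.241)/0.248 = 2.8%. That model was not baseline-adjusted, so this gain comes from retention alone.

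For power, assume 30 per arm, SD 0.25 m/s, ρ = 0.8, effect 0.12 m/s with half present at mid-treatment, and 22% missing. An approximate hand check of the change test:

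- SD of change = 0.25 × √(2 × 0.2) = 0.158 m/s.
- Tested at both visits, per arm = 30 × 0.78 = 23.4.
- SE = 0.158 × √(2/23.4) = 0.046; effect/SE = 0.12/0.046 = 2.6, so power is roughly 70%.

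Simulation (3,000 trials) gave 70.1% for the change test, 73.7% for the same participants with baseline adjustment, and 76.7% for the likelihood model. The total gain is 6.6 points, of which 3.6 come from baseline adjustment and 3.0 from keeping the others. Across the assumed settings the total gain was 2-7 points.

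**The case against.** The strongest reply is that the mixed model is already planned for the same primary outcomes. With categorical time it contains the baseline-to-post contrast, so participants who miss the post test do not leave every efficacy analysis. This stands, and it limits the point to the change-score test and to the missing ranking.

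A reader might infer that the change test is the primary analysis because it is mentioned first. The text states no hierarchy, and the sentence naming the t-test and Mann-Whitney test comes after the mixed models. A reader might also infer that the plan prescribes a completers-only analysis. It does not say so. The restriction follows from the method together with the absence of an imputation rule, and the unabridged protocol may contain one.

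It is also fair to say that the documents give no dropout rate or timing, so how many participants would have mid-treatment data is unknown. The treatment is short, participant and therapist are blinded, and entry criteria screen for endurance. Nothing suggests that dropout would be confined to one arm, and that pattern drives the type I error figures.

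These replies reduce the likely size. They do not settle which analysis answers Aim 1, and an all-randomised label alone would not give a non-returner a change value.

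**Conclusion.** The point holds in a limited form. As written, the change-score test uses only participants tested at both visits. The mixed model can use more of them, and the plan does not rank the two.

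Under the assumed inputs, dropout that depends on early response in the active arm only gives a bias of about 0.01-0.03 m/s and a type I error of about 6-9%, against about 4-5% for the likelihood model. Under a common dropout rule in both arms there is little or no bias, and the loss is about 2-7 points of power, about half of it due to lack of baseline adjustment in the one setting where the two were separated. The actual size cannot be judged without N, SD and dropout.

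The documents do not support the stronger reading that the trial's efficacy result will be biased. The change is worth making because it is cheap.

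**What to change.** State that the Aim 1 pre-to-post estimate is the arm difference at the post-session-10 visit from the planned categorical-time mixed model. It should include all randomised participants as allocated and all available visits, and adjust for baseline gait. Say in advance whether baseline enters as a covariate or as an outcome constrained to be equal between arms. Make the t-test or Mann-Whitney test of change values supportive.

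The cost is a few lines of SAP text and code, with no new data. The downside is that the estimate assumes data are missing at random. The change-score test does not check that assumption: it relies on a stronger one. Any sensitivity analysis should therefore vary the assumption directly, for example by a delta adjustment that shifts the unobserved post values by a range of amounts in each arm.

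### No baseline adjustment is stated for the between-group comparisons of gait speed and paretic single limb stance duration; adjusting would usually gain precision, by an amount the documents do not allow one to fix

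*Combined protocol and SAP*

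**What the plan says.** The Aims 1 and 2 analysis paragraph of the combined protocol and SAP gives the main comparison: "We directly compare pre to post changes for gait speed and paretic single limb stance duration between the two groups". Of the other outcomes it says that "secondary outcome measure changes are being compared between the study groups". The test on change values is given as: "Two-sample comparisons of change values are conducted with t-tests or nonparametric methods such as Mann-Whitney U tests".

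The same paragraph plans a comparison of trajectories "using mixed models and the analysis of Treatment Group by time interaction effects", and on the coding of time it says: "Time is considered as a categorical variable as well as modeled with random slope parameters".

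No baseline covariate is named for any of these analyses, nor a constraint that the two arms share a baseline mean. Baseline variables appear as predictors only in the Aim 3 analysis, which models change in gait and is not the treatment comparison. The Study intervention section lists four assessments: baseline, mid-treatment, after the tenth session, and six weeks later. MRI is done at the first and third.

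**The concern.** A change score subtracts the baseline value with its slope fixed at 1. Under randomization this is unbiased. When the true slope differs from 1, however, an analysis that estimates the slope has smaller variance, apart from a small cost for estimating it. Baseline is already measured, so precision may be left unused on the two gait outcomes and on any outcome taken only at the two MRI visits.

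The planned mixed model does not supply the adjustment as written. With complete data, a categorical-time model with free baseline means gives a baseline-to-post interaction equal to the difference in mean change. The random-slope version uses all visits and is not a pre-post contrast, but it states no adjustment either.

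Chance imbalance is the practical side of this. If the arms differ at baseline, the change-score estimate moves with the difference; an adjusted estimate largely does not.

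**Working it through.** **Inputs.** The documents give no sample size, allocation ratio, SD or pre-post correlation, so there is no figure of the plan's own to reproduce, and every value below is an assumption. N is the total sample size, rho the pre-post correlation, and k = post SD / pre SD. The closed forms take equal arms, a normal baseline, complete data and one baseline slope (rho × k) in both arms.

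**Variance ratio, adjusted (ANCOVA) to change score.**

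Ratio = [k²(1 − rho²) / (1 + k² − 2·rho·k)] × (N − 3)/(N − 4)

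For k = 1 the bracket is (1 + rho)/2. Example: N = 40, rho = 0.7 gives 0.85 × 37/36 = 0.87.

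| N, k | rho 0.5 | 0.7 | 0.8 | 0.9 | 0.95 |
|---|---|---|---|---|---|
| 20, 0.9 | 0.71 | 0.80 | 0.84 | 0.86 | 0.84 |
| 20, 1 | 0.80 | 0.90 | 0.96 | 1.01 | 1.04 |
| 20, 1.1 | 0.87 | 0.98 | 1.03 | 1.06 | 1.04 |
| 40, 0.9 | 0.69 | 0.77 | 0.81 | 0.83 | 0.81 |
| 40, 1 | 0.77 | 0.87 | 0.93 | 0.98 | 1.00 |
| 40, 1.1 | 0.84 | 0.95 | 1.00 | 1.03 | 1.01 |

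Simulation (40,000 trials per cell) agrees with the formula within 0.01, with type I error of 0.048 to 0.052 for both methods.

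**Break-even for k = 1.** Setting the ratio to 1 gives rho = 2(N − 4)/(N − 3) − 1, which is 0.88 at N = 20 and 0.95 at N = 40. Above that, adjustment loses slightly.

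**Worst case under these assumptions.** Since (1 + k² − 2·rho·k) − k²(1 − rho²) = (1 − rho·k)², the bracket is at most 1, reached when the slope is exactly 1. The cap is therefore (N − 3)/(N − 4). The interval-width ratio is the square root of the variance ratio times t(0.975, N − 3)/t(0.975, N − 2).

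| N | Cap on variance ratio | Interval wider by |
|---|---|---|
| 10 | 7/6 = 1.167 | 10.8% |
| 20 | 17/16 = 1.063 | 3.5% |
| 40 | 37/36 = 1.028 | 1.5% |

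**Outside those assumptions.** Suppose that the slopes are 1.2 (active) and 0.9 (sham), with residual SD 0.4, and that the larger arm is active. The simulated ratio is then about 1.11 at 13:7 and 1.09 at 27:13. With slopes of 1.3 and 0.9 it is 1.14 and 1.13. These exceed the caps. With equal arms and slopes of 1.2 and 0.9 it stays close to or below them (about 1.05 at N = 20 and 1.02 at N = 40).

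**Power.** Set the effect so that the change-score t-test has 80% (two-sided 5% assumed). At N = 40 and k = 1, the adjusted analysis has 89%, 85%, 83% and 81% at rho 0.5, 0.7, 0.8 and 0.9. At N = 20, k = 1.1, rho = 0.9 it has 77%.

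**Chance imbalance.** With d ~ Normal(0, 4/N) in baseline SDs, the arms differ by more than 0.3 SD in about 50% of trials at N = 20 and 34% at N = 40. The change-score estimate shifts by (rho·k − 1)·d. For k = 1 and d = 0.3 that is 0.15, 0.09, 0.06 and 0.03 SD in size at rho 0.5, 0.7, 0.8 and 0.9.

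**Mixed model at small N.** In two four-visit settings (complete data, equal correlation between visits), the common-baseline model's post estimate equalled ANCOVA in every dataset checked. Type I error was 0.085 (N = 20) and 0.065 (N = 40) with an uncorrected Wald z-test, against 0.052 and 0.053 with Kenward-Roger.

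**The case against.** The strongest reply is that nothing here is an error. Aim 1 asks about improvement, a change score answers that directly, and each planned test is valid. That stands, and it limits the point to precision.

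A second reply is that the benefit is undetermined. This also stands in part. Hypothesis 3a lists "greater motor abilities of the affected lower extremity" among the baseline factors tied to greater improvement with active stimulation. If motor ability tracks baseline gait, the post SD may exceed the pre SD, and the gain is then smaller or nil over part of the range. Because that hypothesis concerns the active treatment, slopes that differ by arm are also plausible. The loss is then not held to the equal-arm cap unless the arms are close in size, and the allocation ratio is not stated.

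A third reply is that the public text is an abbreviated protocol, so a reader might infer too much from its silence. The documents do not show that the full plan omits adjustment, only that none is stated here.

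Finally, the text is partly in the past tense ("Subjects participated in 10 treatment sessions"), so a new primary analysis chosen now could be post hoc. That governs how the change is made. It does not remove the reason for an adjusted estimate.

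**Conclusion.** The point holds as a precision issue worth considering, with moderate confidence. Adjustment would usually help: at N = 40 with equal SDs it cuts variance by about 23%, 13%, 7% and 2% at rho 0.5, 0.7, 0.8 and 0.9. It gives nothing, or costs a little, when the baseline slope is near 1. The loss is at most 2.8% of variance at N = 40, 6.3% at N = 20 and 16.7% at N = 10, given equal arms, a normal baseline and a common slope. It was about 9% to 14% in the assumed examples with unequal arms and different slopes. N, rho, the SD ratio and the allocation ratio are all absent from the documents.

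Two stronger readings are not supported. One is that the planned comparison is biased or invalid: randomization protects it. The other is that adjustment is a sure gain at a small cost whatever the design: both gain and cost depend on quantities that the documents do not give.

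**What to change.** If analysis has not begun:

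- For each of the two gait outcomes, make primary the baseline-adjusted active-minus-sham difference at the post-treatment visit, with its confidence interval. Use ANCOVA (post on group and baseline) or, equivalently with complete data, the planned categorical-time mixed model with a common baseline mean and a small-sample correction such as Kenward-Roger.
- Use ANCOVA for outcomes measured only at the two MRI visits.
- If allocation is clearly unequal, centre baseline and include a group-by-baseline term, or use robust standard errors.
- Keep the change-score t-test and the Mann-Whitney U test as sensitivity analyses.

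If analysis has begun, keep the planned analysis primary and report the adjusted one beside it, labelled as added later. If the full protocol already specifies an adjustment, stating it resolves the point.

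No new data, visits or participants are needed. The costs are the possible small loss of precision set out above, the need for a small-sample correction in the mixed model and, if the change comes late, a risk of post hoc selection that must be disclosed.
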